### 9.2.3 Medical History

Medical history will be coded by using the Medical Dictionary for Regulatory Activities (MedDRA). For the FAS, medical history will be summarized descriptively by system organ class and preferred term. The corresponding data listing will also be provided.

In addition, the number of subjects reported to have had positive cultures for respiratory pathogens within the 2 years prior to screening (i.e., answered yes on the respiratory microbiology form) will be summarized for the FAS. The corresponding data listing will be provided. Hospitalization and clinic visit history in the year prior to the signing of informed consent will be listed.

### 9.2.4 Prior and Concomitant Medications

Medications will be coded using the World Health Organization Drug Dictionary (WHO-DD) and categorized as follows:

**Prior medication:** any medication that was administered during the 56 days prior to the first dose of study drug in the Treatment Period but not in the Run-in Period.

**Concomitant medication during the Run-in Period:** medication continued or newly received during the TE period for the Run-in Period.

**Concomitant medication during the Treatment Period:** medication continued or newly received during the TE period for the Treatment Period.

**Post-treatment medication:** medication continued or newly received after:

- the TE period for the Run-in Period if the subject did not receive study drug in the Treatment Period.
- the TE period for the Treatment Period for subjects who received study drug in the Treatment Period.

A given medication may be classified as any combination of the above categories, for example, prior and concomitant during the Run-in Period, concomitant during the Treatment Period and post-treatment, or concomitant for both periods and post-treatment.

If a medication has completely missing or partially missing start/stop date and if it cannot be determined whether it was taken before the first dose date of study drug, concomitantly, or after the TE period, it will be classified as prior, concomitant for both periods, and post-treatment. Details for imputing missing or partial start and/or stop dates of medication are described in [Appendix B](#).

Prior medications and concomitant medications will be summarized descriptively for FAS using frequency tables by: 1) treatment group and overall, preferred name (PN); and 2) treatment group and overall, anatomic class (ATC) level 1, ATC level 2, and PN.

Prior and concomitant medication during the Run-in Period will be summarized together in one summary table. Post-treatment medications will be listed in the all medication listing.

### 9.2.5 Study Drug Exposure

Study drug exposure will be summarized for the Treatment Period only based on the Safety Set for the Treatment Period, and will be presented by treatment group and overall.

Duration of study drug exposure (in days) will be calculated as: last dose date of study drug in the Treatment Period – first dose date of study drug in the Treatment Period + 1, regardless of study drug interruption, and will be summarized descriptively.

Study drug exposure (in weeks) will be summarized descriptively by the number of subjects (n), mean, SD, median, min, and max. It will also be summarized by interval:  $\leq 2$  weeks,  $>2- \leq 4$  weeks, and  $> 4$  weeks, using counts and percentages. Additionally, the total study drug exposure, defined as the sum total of the study drug exposure across all subjects (in patient-weeks), will be provided.

### **9.2.6 Study Drug Compliance**

Study drug compliance will be summarized for the Treatment Period only based on the FAS, and will be presented by treatment group and overall.

Study drug compliance will be calculated as:  $100 \times [1 - (\text{total number of days of study drug interruption during the Treatment Period}) / (\text{duration of study drug exposure in days during the Treatment Period})]$ . A study drug interruption on a given day is defined as an interruption of any study drugs on that day. A study drug interruption that continues through the end of the study participation (i.e., subject does not resume study drug before the end of the study participation) will not be included in the compliance calculation.

Study drug compliance will be summarized descriptively by the number of subjects (n), mean, SD, median, min, and max. It will also be summarized in categories:  $<80\%$  and  $\geq 80\%$  using frequency tables.

In addition, percentage of tablets taken will be calculated using the following formula:  $100 \times [(\text{total number of tablets dispensed for the Treatment Period}) - (\text{total number of tablets returned for the Treatment Period})] / (\text{total number of tablets planned to be taken per day} \times \text{duration of study drug exposure in days for the Treatment Period})$ . Summary similar to those for the study drug compliance will be produced based on the FAS.

### **9.2.7 Important Protocol Deviations**

An important protocol deviation (IPD) is a deviation that may significantly affect the completeness, accuracy, or reliability of the study data or that may significantly affect a subject's rights, safety, or well-being. IPD rules will be developed and finalized before database lock.

The protocol deviations that should be considered as potential IPDs include, but are not limited to:

- Subject was enrolled in the study despite the violation of inclusion/exclusion criteria
- Subject was less than 80% compliant with study drug for non-safety reasons
- Subject received prohibited concomitant medications
- Subject received the wrong treatment or incorrect doses
- Subject remained in the study despite meeting withdrawal criteria

Occurrence of any of these events should be considered as potential IPDs, but a blinded team should categorize them as IPDs only if they have the potential to significantly affect the

completeness, accuracy, or reliability of the study data or that may significantly affect a subject's rights, safety, or well-being.

IPDs (from the clinical database or from the site deviation log) will be summarized descriptively based on the FAS and presented by treatment group and overall. Additionally, IPDs will be provided in an individual subject data listing.

### **9.3 Efficacy Analysis**

Unless otherwise defined, all efficacy analyses described in this section will be based on the FAS.

#### **9.3.1 Analysis of Primary Efficacy Variable**

##### **9.3.1.1 Definition of Variable**

The primary efficacy variable is the absolute change in ppFEV1 from baseline at Week 4.

Percent predicted FEV1 is the ratio of FEV1 (L) to the predicted FEV1 (L), expressed as a percentage. The predicted FEV1 will be calculated using the Global Lung Function Initiative (GLI); details are in [Appendix C](#).

##### **9.3.1.2 Primary Analysis**

The primary analysis will be performed using a mixed-effects model for repeated measures (MMRM) with the absolute change from baseline at Day 15 and Week 4 as the dependent variable. The model will include treatment group, visit, and treatment-by-visit interaction as fixed effects, with continuous baseline ppFEV1, and age at screening (<18 versus ≥18 years of age) as covariates. The model will be estimated using restricted maximum likelihood. Denominator degrees of freedom for the *F*-test for fixed effects will be estimated using the Kenward-Roger approximation. An unstructured covariance structure will be used to model the within-subject errors. If the model estimation does not converge, a compound symmetry covariance structure will be used instead. Conditional on the observed data and covariates, missing data will be assumed to be missing at random; consequently, no imputation of missing data will be performed.

The primary result obtained from the model will be the estimated treatment difference at Week 4. The adjusted means with 2-sided 95% confidence intervals and 2-sided *P* values will be provided. Furthermore, the treatment difference at each post-baseline visit obtained from the model will also be provided.

The adjusted mean (with SE) obtained from the MMRM analysis at each post-baseline visit up to Week 4 will be plotted by treatment group.

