^d Any female subject who does not meet the criteria for non-childbearing potential is considered to be of childbearing potential and must have a serum pregnancy test. A definition of non-childbearing potential is provided in [Section 11.7.7.1](#).

^e Weight and height will be measured with shoes off.

^f Ophthalmologic examinations will be conducted only for subjects who are <18 years of age on the date of informed consent. For subjects with documentation of bilateral lens removal, ophthalmologic examinations are not required. The ophthalmologic examination does not need to be conducted if there is documentation of an examination meeting the protocol requirements that was conducted within 3 months before the date of informed consent ([Section 11.7.6](#)). The ophthalmologic examination will be conducted by a licensed ophthalmologist or optometrist.

^g Vital signs and pulse oximetry will be collected after the subject has been at rest for at least 5 minutes.

^h A standard 12-lead ECG will be performed after the subject has been at rest for at least 5 minutes.

ⁱ Spirometry may be performed pre- or post-bronchodilator ([Section 11.6.1](#)).

^j Refer to [Section 9.5](#) for details.

Table 3-2 VX17-659-103: TEZ/IVA Run-in Period, Treatment Period, and Safety Follow-up Visit

Event/Assessment ^a	TEZ/IVA Run-in Period (4 Weeks)		Treatment Period (4 Weeks)			ETT Visit ^b	Safety Follow-up Visit 28 (± 7) Days After the Last Dose of Study Drug (If Applicable) ^c
	Day -28 ± 1 Day	Day -14 (Day -15 to Day -3)	Day 1 ^d	Day 15 ± 3 Days	Week 4 ± 5 Days		
Clinic visit	X	X	X	X	X	X	X
Inclusion and exclusion criteria confirmation	X						
CFQ-R ^e			X	X	X	X	X
Weight and height ^f	X		X	X	X	X	X
Physical examination ^g	Abbreviated		Complete		Complete	Complete	
Pregnancy testing ^h	Urine		Urine		Urine	Serum	Serum
Standard 12-lead ECG ⁱ	X		X	X	X	X	X

^a All assessments will be performed before dosing unless noted otherwise.

^b If the subject prematurely discontinues study drug treatment, an ETT Visit should be scheduled as soon as possible after the decision to discontinue treatment. Subjects who prematurely discontinue treatment during the Treatment Period will continue to complete all scheduled study visits for assessments following completion of the ETT Visit (Section 9.1.5.2).

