^r Randomization may occur on either Day -1 or Day 1, after conditions for entry into the Treatment Period ([Section 9.1.3](#)) have been satisfied. Randomization must occur before the first dose of study drug in the Treatment Period.

^s For the Treatment Period, the randomized study drug regimen should be administered as outlined in [Section 9.6.1](#). On days of scheduled visits, refer to [Section 9.6.1](#) for the timing of dosing relative to the assessments. The final dose of study drug in the Treatment Period will be administered the evening before the Week 4 Visit.

[figure not shown]
██████████ Completion of study participation is defined in [Section 9.1.7](#).

^v SAEs that occur after completion of study participation and are considered related to study drug will be reported to Vertex GPS within 24 hours as described in [Section 13.1.2.2](#).

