9.3 Rationale for Study Design and Study Drug Regimens

9.3.1 Study Design

This Phase 3 study will assess the efficacy, PD, safety, and PK of VX-659/TEZ/IVA TC therapy in subjects with CF who have an F/F genotype.

A randomized, double-blind, controlled study design was selected to ascertain the effects of VX-659/TEZ/IVA while avoiding observer bias. TEZ/IVA is considered an appropriate active control since the efficacy and safety of TEZ/IVA in F/F subjects have been demonstrated in Study VX14-661-106 (Study 661-106).¹⁴ Study 661-106 met its primary endpoint of absolute change in ppFEV₁ through Week 24, with a 4.0 percentage point treatment difference between TEZ/IVA and placebo. In Study 661-106, TEZ/IVA was well tolerated and no safety concerns attributable to TEZ/IVA were identified.

A 4-week TEZ/IVA Run-in Period was incorporated into this study to establish a reliable on-treatment (TEZ/IVA) baseline for comparison during the Treatment Period.

[figure not shown]
The study will have a 4-week treatment duration because previous studies of CFTR modulators (IVA, LUM/IVA, and TEZ/IVA) have demonstrated that efficacy related to lung function (ppFEV₁) can be reliably established using an endpoint at Week 4. In these studies, rapid improvements in ppFEV₁ are observed by Day 15, with a separation between the active treatment and placebo groups that is sustained through 24 weeks of treatment. These studies were conducted in patients with different genotypes, baseline ppFEV₁, and age groups, using CFTR modulators that had different magnitudes of response.

The extent of response to CFTR modulator treatment may depend on the subject's ppFEV₁ value (an index of disease severity) before the start of TC study drug dosing. Some subjects in this study may be receiving treatment with LUM/IVA or TEZ/IVA at Screening, while some subjects may not be receiving treatment with CFTR modulators. Therefore, randomization will be stratified by ppFEV₁ value determined during the TEZ/IVA Run-in Period after at least 13 days of TEZ/IVA (Day -14 assessment). Randomization will also be stratified by age at screening. This will ensure a balanced evaluation of adult and pediatric subjects.

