11.6 Efficacy

11.6.1 Spirometry

Spirometry will be performed according to the American Thoracic Society Guidelines/European Respiratory Society Guidelines¹⁰ and according to the additional guidelines that follow.

Pre-bronchodilator spirometry is defined as spirometry testing performed for subjects who have

- withheld their short-acting bronchodilators (e.g., albuterol) or anticholinergic (e.g., ipratropium bromide [Atrovent®]) for more than 4 hours before the spirometry assessment;
- withheld their long-acting bronchodilator (e.g., salmeterol) for more than 12 hours before the spirometry assessment; and
- withheld their once-daily, long-acting bronchodilator (e.g., tiotropium bromide [Spiriva®]) for more than 24 hours before the spirometry assessment.

During the Screening Period, spirometry assessments may be performed pre- or post-bronchodilator. At all other visits, all spirometry assessments should be performed pre-bronchodilator. During the Treatment Period, spirometry assessments must be performed before study drug dosing ([Section 9.6.1](#)) at approximately the same time at each visit. In the

event that a subject forgets to withhold bronchodilator(s), spirometry should be performed according to the following:

- If a subject's Day 1 spirometry assessment is pre-bronchodilator, but, on a subsequent visit, the subject forgets to withhold bronchodilator use, a post-bronchodilator spirometry assessment will be obtained for that visit only, and the visit will not be rescheduled.
- If, on Day 1, the subject forgets to withhold his/her dose of bronchodilator, spirometry should be performed post-bronchodilator, and all subsequent spirometric measurements (according to the schedule of assessments in [Table 3-2](#)) should be performed post-bronchodilator.
- Each spirometry assessment will be recorded in the source documents as pre- or post-bronchodilator.

All sites will be provided with spirometers to be used for all study assessments. Spirometry data will be transmitted to a centralized spirometry service for quality review. The investigator's assessment of the spirometry results will be used for the screening assessment and determination of eligibility.

See [Section 10.7.1](#) for information about access to spirometry results.

The measured spirometric values listed below will be converted to percent predicted values using the standard equations of GLI.⁹

- FEV₁ (L)

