12.3.3.1 Analysis of Primary Variable

The primary efficacy variable is the absolute change in ppFEV₁ from baseline at Week 4. The analysis of this variable will be performed using a mixed-effects model for repeated measures (MMRM) with absolute change from baseline in ppFEV₁ at Day 15 and Week 4 as the dependent variable. The model will include treatment group, visit, and treatment-by-visit interaction as fixed effects, with continuous baseline ppFEV₁ and age at screening (<18 versus ≥18 years of age) as covariates. The model will be estimated using restricted maximum likelihood.

Denominator degrees of freedom for the *F* test for fixed effects will be estimated using the Kenward-Roger approximation. An unstructured covariance structure will be used to model the within-subject errors. If the model estimation does not converge, a compound symmetry covariance structure will be used instead. Conditional on the observed data and covariates, missing data will be assumed to be missing at random; consequently, no imputation of missing data will be performed.

The primary result obtained from the model will be the estimated treatment difference at Week 4. The adjusted mean with a 2-sided 95% CI and a 2-sided *P* value will be provided. Furthermore, the treatment difference at each post-baseline visit will also be provided, obtained from the model.

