### 7.3 Randomization

Randomization will be stratified by ppFEV1 determined during the TEZ/IVA Run-in Period (Day -14 assessment; <70 versus ≥70) and age at the Screening Visit (<18 versus ≥18 years of age). If the Day -14 ppFEV1 value is not valid or not available, the most recent available ppFEV1 value will be used for stratification.

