## 9 STATISTICAL ANALYSIS

### 9.1 General Considerations

The Schedule of Assessments is provided in Section 3 of CSP. The precision standards for reporting safety and efficacy variables are provided in an internal Biometrics document that specifies the programming rules including the precision for derived variables.

**Continuous variables** will be summarized using the following descriptive summary statistics: the number of subjects (n), mean, SD, median, minimum value (min), and maximum value (max).

**Categorical variables** will be summarized using counts and percentages. Percentages will be presented to 1 decimal place.

**Baseline value**, unless otherwise specified, is defined as the most recent non-missing measurement (scheduled or unscheduled) collected before the first dose of study drug in the Treatment Period.

**Absolute change** from baseline will be calculated as post-baseline value – baseline value.

**Relative change** from baseline will be calculated as (post-baseline value – baseline value)/baseline value.

The **Treatment-emergent (TE) Period for the Run-in Period** will be from the first dose of study drug in the Run-in Period to (1) the first dose of study drug in the Treatment Period for subjects who complete the Run-in Period and continue to the Treatment Period, or (2) 28 days after the last dose date of study drug in the Run-in Period for subjects who do not continue to the Treatment Period (e.g., subjects who do not meet the conditions to enter the Treatment Period).

The **TE Period for the Treatment Period** will include the time from the first dose date of study drug in the Treatment Period (TC or placebo + TEZ/IVA) to 28 days after the last dose of the study drug or to the completion of study participation date, whichever occurs first.

Completion of study participation for each individual subject is defined as one of the following:

- For subjects who complete the Treatment Period and enter an open-label study within 28 days of the Week 4 Visit: the Week 4 Visit
- For subjects who complete the Treatment Period and do not enter an open-label study within 28 days of the Week 4 Visit: the Safety Follow-up Visit
- For subjects who prematurely discontinue study drug treatment during the Treatment Period but do not withdraw consent (and assent, as applicable): The ETT or Safety Follow-up Visit (if required)

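### The primary MMRM does not use the Day -14 on-TEZ/IVA ppFEV1 already collected; as a second covariate it would plausibly cut residual variance by about 5-12%

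*SAP*

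**What the plan says.** The primary model is the same in both documents. Protocol 12.3.3.1 states: "The model will include treatment group, visit, and treatment-by-visit interaction as fixed effects, with continuous baseline ppFEV₁ and age at screening" group. SAP 9.3.1.2 has the same terms, "with continuous baseline ppFEV 1 , and age at screening (<18 versus ≥18 years of age) as covariates". The synopsis agrees.

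The baseline value "is defined as the most recent non-missing measurement (scheduled or unscheduled) collected before the first dose of study drug in the Treatment Period" (SAP 9.1). That is a single reading, normally the Day 1 pre-dose one.

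A second on-treatment reading exists. Protocol 9.1.2 schedules spirometry at Day -14, and Protocol 9.3.1 says this comes after at least 13 days of TEZ/IVA. Table 3-2 allows the visit anywhere from Day -15 to Day -3. Its bronchodilator condition is meant to match Day 1: "During the Screening Period, spirometry assessments may be performed pre- or post-bronchodilator. At all other visits, all spirometry assessments should be performed pre-bronchodilator" (Protocol 11.6.1). Its stated use is stratification: "Randomization will be stratified by ppFEV 1 determined during the TEZ/IVA Run-in Period (Day -14 assessment; <70 versus ≥70) and age at the Screening Visit" (SAP 7.3). SAP 9.2.2 also tabulates the <70/≥70 category.

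For the two key secondary endpoints, SAP 9.3.2.2 lists baseline ppFEV1 and age group as covariates. It does not list baseline sweat chloride or baseline CFQ-R respiratory domain score.

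**The concern.** The run-in is there to give a reliable on-TEZ/IVA baseline (Protocol 9.1.2 and 9.3.1). One spirometry reading carries within-subject noise, so a covariate built on Day 1 alone is an imperfect measure of the subject's stable level. The Day -14 reading measures the same level, on the same background treatment, before randomization. Using it as a covariate changes neither the endpoint nor the baseline definition, and it cannot bias the randomized comparison. What is at stake is the width of the confidence interval for the primary difference, and some protection if the true effect is below 5 points or the SD above 7.

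The <70/≥70 stratum is the smaller part of this. Continuous baseline ppFEV1 already carries most of that information.

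**Working it through.** **1. The plan's own figure.** Inputs from SAP 7.2: SD of change 7, difference 5.0, 50 per arm, 5% dropout, 2-sided alpha 0.05. With 50 × 0.95 = 47.5, take 47 per arm. The noncentrality is 5 / (7 × √(2/47)) = 5 / 1.444 = 3.46 on 92 df. Power is 92.9%, or 93.1% at 47.5 per arm. The stated value of approximately 93% reproduces and needs no covariate adjustment.

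**2. Assumptions that are not in the documents.** Stable between-subject SD S of 12-16 points. Four patterns for the change variance of 7² = 49:
- (a) all independent visit noise;
- (b) half noise, half drift;
- (c) half variable response, the remainder split equally between noise and drift;
- (d) pure serial correlation.

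Drift half-life is 7-56 days and Day -14 is 14 days before Day 1.

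**3. Pattern (a) by hand.** Noise variance per visit is v = 49/2 = 24.5.
- Given Day 1 only, residual variance = v + S²v/(S² + v). S = 12: 24.5 + 144 × 24.5/168.5 = 45.4. S = 16: 24.5 + 256 × 24.5/280.5 = 46.9.
- Given Day 1 and Day -14, residual variance = v + S²(v/2)/(S² + v/2). S = 12: 24.5 + 144 × 12.25/156.25 = 35.8. S = 16: 24.5 + 256 × 12.25/268.25 = 36.2.
- Cut: 21% at S = 12 and 23% at S = 16. As S grows it tends to 1 − 36.75/49 = 25%, so 23% is not a hard ceiling.

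**4. All patterns** (47 per arm, difference 5; baseline only → Day -14 added):

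| Pattern | Residual variance | Cut | Power, % | 95% CI half-width |
|---|---|---|---|---|
| (a) | 45.4-46.9 → 35.8-36.2 | 21-23% | 93.9-94.5 → 97.9-98.0 | 2.76-2.81 → 2.45-2.47 |
| (b) | 45.5-47.1 → 37.4-42.7 | 9-19% | 93.8-94.5 → 95.6-97.5 | 2.76-2.81 → 2.51-2.68 |
| (c) | 48.0-48.5 → 43.5-46.1 | 5-10% | 93.1-93.3 → 94.2-95.3 | 2.84-2.85 → 2.70-2.78 |
| (d) | 45.4-46.9, unchanged | 0% | unchanged | unchanged |

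If the Day -14 visit falls only 3 days before Day 1, the maximum drops from 19% to 14% in (b) and from 10% to 7% in (c). The <70/≥70 stratum alone gives 3-7% (a), 1-5% (b), 0.3-1.7% (c) and 0% (d), at an assumed mean ppFEV1 of 55-68.

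**5. Simulation of the Day 15/Week 4 MMRM.** REML, unstructured covariance, 4,000 runs per cell, 100 randomized, S = 14, half-life 14 days. Assumed: 6% missing Week 4, 5% missing Day -14, and 3% with Day -14 as the baseline. The last two were filled as described under the fix. Degrees of freedom were approximate, not Kenward-Roger. The variance change is (width ratio)² − 1.

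| Pattern | CI full width | Variance change | Power, % |
|---|---|---|---|
| (a) | 5.59 → 5.01 | −20% | 94.0 → 97.6 |
| (b) | 5.57 → 5.22 | −12% | 94.0 → 96.6 |
| (c) | 5.68 → 5.50 | −6% | 93.4 → 95.0 |
| (c), 3-day gap | 5.68 → 5.54 | −5% | 92.9 → 94.1 |
| (d) | 5.62 → 5.64 | +0.7% | 94.3 → 94.1 |

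Type I error stayed between 4.3% and 5.4%, with Monte Carlo error of about 0.4 points.

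**6. Key secondary outcomes.** With equal variances σ² and correlation ρ between baseline and Week 4, the variance of change is 2σ²(1 − ρ), and given the outcome's own baseline it is σ²(1 − ρ²). The cut is (1 − ρ)/2, that is 25%, 15% and 5% at assumed ρ of 0.5, 0.7 and 0.9. This takes the listed covariates as explaining none of the change. It is not counted in the figures above.

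**The case against.** The planned analysis needs no rescue. Protocol and SAP agree on it, it adjusts for age group and continuous ppFEV1, and its power comes from an unadjusted t-test. One pre-dose baseline is a defensible choice. All of this stands, and it limits the point to an optional improvement.

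The top of the range is also fragile. It needs every part of the SD of 7 to be independent visit noise. Protocol 9.3.1 points the other way: "The extent of response to CFTR modulator treatment may depend on" the subject's ppFEV1 before triple-combination dosing. If half of the change variance is variable response, the cut is 11-12% even with no drift, and 5-10% with drift. This stands too, and it is why 5-12% is the size given here.

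Three stronger readings are tempting, and the documents support none of them. A reader might infer that omitting a stratification factor makes the model wrong, but continuous baseline ppFEV1 covers most of that factor and the comparison remains valid. A reader might infer that the trial is underpowered, but the stated power reproduces without any covariate. A reader might infer that no supportive analysis uses Day -14. That cannot be judged: the SAP contents list runs section 9.3.1 from page 14 to page 16 with little of it visible, and reference 6, on multiply imputed data, has no visible citation. The primary model paragraph itself is visible in full.

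**Conclusion.** The omission is real and cheap to repair, but it is not an error. Adding continuous Day -14 ppFEV1 would plausibly cut residual variance by about 5-12%. That makes the confidence interval about 3-6% narrower (√0.95 = 0.975, √0.88 = 0.938). The range runs from a loss of under 1% under pure serial correlation to about 20-23% if all change variance is independent visit noise. Every one of these figures rests on the assumed between-subject SD and visit correlations. With about 93% power already planned, the main benefit is a tighter estimate. The missing outcome baselines in the two key secondary models are a separate item of the same kind.

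**What to change.** Before database lock and unblinding, add continuous Day -14 ppFEV1 to the covariate list in SAP 9.3.1.2, next to continuous baseline ppFEV1 and age group. Match Protocol 12.3.3.1 and the synopsis.

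Add one rule. If Day -14 ppFEV1 is missing, invalid or is itself the baseline value, replace it with its prediction from a linear regression on baseline ppFEV1 and age group. Fit that regression to FAS subjects with both values, pooled over arms, using only data collected before the first dose in the Treatment Period. The limit has to be the first dose and not randomization: "Randomization may occur on either Day -1 or Day 1" (Protocol Table 3-2, footnote r), so the Day 1 baseline can fall after randomization. The rule fills a covariate only; outcomes stay unimputed. The stratification fallback should not be reused, because the most recent available value may be a post-bronchodilator Screening reading or Day 1 itself.

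If a protocol modification is unwelcome, prespecify this model in the SAP as a supportive analysis.

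Separately, in SAP 9.3.2.2 add continuous baseline sweat chloride to the sweat chloride model and continuous baseline CFQ-R respiratory domain score to the CFQ-R model.

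Cost: about one degree of freedom per covariate, the missing-covariate rule and an SAP amendment (SAP 4). Matching the protocol text also needs investigator and sponsor approval and regulatory submission (Protocol 13.2.3). No new visits, data or patients are needed. If Day -14 adds nothing, the simulated CI full width goes from 5.62 to 5.64 points.
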